### 9.0 Local Number of Participants

9.1 Local Number of Participants to be Consented: 65 (Our goal is to randomize 44 participants. From previous experience, we expect no more than 15% to fail inperson screening after consent is obtained.)

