| Lifestyle therapy (virtual)                    |             |                                                 | Х                  |                    | X                  |                    | Х                   |                     | X                   |              | X                   |                     | X                   |                     |
| ,                                              |             |                                                 |                    |                    |                    |                    |                     |                     |                     |              |                     |                     |                     |                     |

- Blood or urine pregnancy tests can be conducted at the Screening and Week 24 visits. Urine pregnancy tests will be done at the Baseline/Randomization. Week 4, Week 8, Week 12, Week 16 and Week 20 visits.
- Accelerometer will be worn 24/hours x 7 days between screening and baseline and again for 24/hours x7 days between Week 20 and Week 24
- 3. Participant may be given a placebo test capsule to ensure they are able to swallow the capsules for the study
- 4. Barkley Rating Scales will be performed every two weeks during the dose escalation through Week 10 and then at the in person visits (Weeks 12, 16, 20 and 24).
- 5. Basic metabolic panel to consist of anion gap, calcium, chloride, bicarbonate, creatinine, glucose, potassium, sodium, urea nitrogen
- 6. Only BAS will be utilized
- 7. Baseline/Randomization must occur within 21 days of the date blood was drawn at the Screening visit.

PROTOCOL TITLE: Lisdexamfetamine for the Treatment of Severe Obesity in Children Aged

6 to 12 Years

VERSION DATE: 19Sep2025

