#### 7.2 Exclusion Criteria:

- Contraindications to lisdexamfetamine, including current or recent (< 14 days) use of monoamine oxidase inhibitor and known hypersensitivity to amphetamine products.

- Family history of sudden death or ventricular arrhythmia in any first or second degree relative with any of the following: sudden or unexplained death including sudden infant death syndrome, cardiomyopathy, heart transplant, familial arrhythmia (such as Wolff-Parkinson-White syndrome, long QT interval, or implantable defibrillator).
- Any history of fainting or seizure from exercise, startle or fright
- Clinically significant congenital or structural heart disease or arrhythmia.
- BMI < 1.2 times the 95th percentile at the baseline/randomization visits
- Hypertension defined as SBP and/or DBP >95th percentile (on 3 separate occasions) at the screening OR baseline/randomization visits.
- Tachycardia defined HR >120 bpm (on 3 separate occasions) at the screening OR baseline/randomization visits.
- Current or recent (< 3 months) use of psychostimulant or sympathomimetic amine.
- History of chemical dependency.
- Diabetes mellitus (type 1 or 2).
- Current or recent (< 3 months) use of anti-obesity medication(s).
- Previous bariatric surgery.
- Recent initiation or change in dose (< 3 months prior) of anti-hypertensive or lipid medication(s).
- TSH > 1.5x ULN.
- AST or ALT > 3x ULN.
- Fasting glucose ≥ 126 mg/dL
- History of mania, schizophrenia, bipolar disorder, or psychosis.
- Unstable depression or anxiety that has required hospitalization in the past 12 months.
- Any history of suicide attempt.

PROTOCOL TITLE: Lisdexamfetamine for the Treatment of Severe Obesity in Children Aged 6 to 12 Years

VERSION DATE: 19Sep2025

- Columbia Suicide Severity Rating Scale (C-SSRS) with a score of Moderate or High at the screening or baseline/randomization visits.
- Children's Depressive Inventory 2 (CDI-2) score ≥ 70 (based on parent or child report) at the screening or baseline/randomization visits.
- Concomitant use of tricyclic antidepressants, selective serotonin reuptake inhibitors (SSRIs), serotonin and norepinephrine reuptake inhibitors (SNRIs), lithium, fentanyl, tramadol, triptans, tryptophan, buspirone, and St. John's wort at any time during the study.

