#### 11.0 Withdrawal of Participants

- 11.1 Withdrawal Circumstances: Participants will be allowed to withdraw from the study at any time. Participants will be asked to return for one final visit and to return any study medication. Participants may be withdrawn from the study at any time based upon investigator judgement.
- 11.2 Withdrawal Procedures: Any participant who is removed from the study by the principal investigator will be asked to return for one final visit to assess adverse events and to collect any unused study medication and do a final study medication compliance.
- 11.3 Termination Procedures: It will be noted in the subject enrollment log that the participant has been discontinued from the study and the date of the last study related visit. No additional data will be collected after that time. Data that has already been collected can be used in the study analysis.

PROTOCOL TITLE: Lisdexamfetamine for the Treatment of Severe Obesity in Children Aged

6 to 12 Years

VERSION DATE: 19Sep2025

11.4

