| Table 1. Exa           | imples of chan             | ges in BMI and co                   | rresponding o            | changes in %BMIp                    | 95                                   |                                  |
|------------------------|----------------------------|-------------------------------------|--------------------------|-------------------------------------|--------------------------------------|----------------------------------|
| Example
Participant | Starting
BMI
(kg/m²) | Starting
%BMIp95                 | Ending
BMI
(kg/m2) | Ending
%BMIp95                   | Absolute
change in
BMI (kg/m2) | Absolute
change in
%BMIp95 |
| 6 yo girl              | 26.37                      | 140% of 95 th percentile | 25.2                     | 134% of 95 th percentile | -1.17                                | -6 percentage points             |
| 10 yo boy              | 39.8                       | 135% of 95 th percentile | 28.7                     | 130% of 95 th percentile | -1.1                                 | -5 percentage points             |

Power Analysis: Given this is a pilot and feasibility study, the sample size is not driven by a power analysis stemming from a formal statistical evaluation of a hypothesis test associated with the primary endpoint the trial. Instead, the objectives of this study revolve around identifying key information on execution of the study and experience of participants to best inform the design of a subsequent, larger study to examine efficacy and effectiveness.

Secondary endpoints for Aim 1 are also continuous and will be evaluated in a similar fashion, with adjustment for baseline value. These include percent body fat, lab measurements of glucose, insulin, lipids (total-, LDL-, HDL-cholesterol, and

PROTOCOL TITLE: Lisdexamfetamine for the Treatment of Severe Obesity in Children Aged

6 to 12 Years

VERSION DATE: 19Sep2025

triglycerides), hemoglobin A1c, ALT, AST, and PedsQL. We will also report on other metrics of BMI change, including absolute BMI change and percent BMI change.

**Aim 2:** Generate estimates of the tolerability and safety of LDX used for the treatment of severe obesity in children.

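### Does a consent target of 65 conflict with 44 randomised and at most 15% screen failure?

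*Combined protocol and SAP*

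**What the plan says.** Section 9.1 of the protocol gives three figures together: "Local Number of Participants to be Consented: 65", then "Our goal is to randomize 44 participants", and then, citing previous experience, "we expect no more than 15% to fail inperson screening after consent is obtained". It gives no formula, no second loss rate and no safety margin. The revision history says that the latest revision (19 September 2025) adjusted the number to be consented so as to reach 44 randomised, without giving a rate.

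Other sections show that children can also be lost after they pass screening. Several exclusions in section 7.2 are applied again at baseline, for example a suicide-risk rating "with a score of Moderate or High at the screening or baseline/randomization visits". BMI, blood pressure, heart rate and the depression score are also checked at baseline. Footnote 7 to the schedule of events in section 4.1 adds a time limit: "Baseline/Randomization must occur within 21 days of the date blood was drawn at the Screening visit". Section 11.1 states that "Participants will be allowed to withdraw from the study at any time".

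Section 14.0 says that the sample size does not rest on a power calculation and that the study's objectives concern "identifying key information on execution of the study and experience of participants to best inform the design of a subsequent, larger study".

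**The concern.** The 15% stands in the same parenthesis as the goal of 44, directly after the 65, so a reader takes it as the reason for the 65. It does not produce that number. Because 15% is stated as a maximum, a lower true rate would widen the gap: at 10% failure the expected need is 44/0.90 = 48.9, or 49.

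Two things could be at stake. First, an ethics committee might ask why 13 more children (65 − 52) would be consented and screened, with a fasting blood draw, an ECG and Tanner staging, than the stated rate needs on average. Second, the trial is a pilot meant to inform a larger study, and the yield from consent to randomisation is one of the things a pilot can teach. Someone who budgeted the larger trial from the 15% would allow 1/0.85 = 1.18 consents per child randomised, while the protocol's own ratio is 65/44 = 1.48. If the latest revision raised the consent number because losses were running higher than expected, the 15% beside it may be out of date.

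**Working it through.** **Inputs** (section 9.1): consents n = 65, randomisation target 44, screen failure at most 0.15.

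**Step 1. Try to reproduce 65.**
- Expected need: 44/(1 − 0.15) = 51.8, so 52.
- Adding 15% to the target instead: 44 × 1.15 = 50.6, so 51.
- Expected number passing out of 65: 65 × 0.85 = 55.3, about 11 above 44.

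Neither formula gives 65.

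**Step 2. Allow for chance.** Let X be the number passing among n consented, binomial with probability 0.85, and compute P(X ≥ 44).

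| Consents n | P(X ≥ 44) at 15% failure |
|---|---|
| 52 | 62.3% |
| 56 | 93.2% |
| 57 | 96.1% |
| 60 | 99.4% |
| 63 | 99.94% |
| 65 | 99.99% |

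An ordinary margin of 90% or 95% would need 56 or 57, and even 99.9% assurance needs only 63. Screening failure at 15% plus a usual margin does not explain 65 either.

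**Step 3. Ask what total loss 65 could cover.** Let q be the total loss from consent to randomisation.
- With no margin, q = 1 − 44/65 = 32.3%. If 15% of that falls at screening, the further loss among those who pass is 1 − 44/(65 × 0.85) = 1 − 44/55.25 = 20.4%.
- With a margin, solve P(Bin(65, 1 − q) ≥ 44) = target. The further loss after screening is then 1 − (1 − q)/0.85.

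| Assurance of reaching 44 | Total loss q | Further loss after 15% at screening |
|---|---|---|
| no margin | 32.3% | 20.4% |
| 90% | 26.0% | 13.0% |
| 95% | 24.1% | 10.8% |
| 97.5% | 22.6% | 8.9% |
| 99% | 20.8% | 6.8% |
| 99.9% | 17.4% | 2.8% |

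The documents state none of these assurance levels. The loss consistent with 65 thus runs from 32% down to 17% according to a choice the protocol does not report, and if 65 is a ceiling it implies no loss rate at all.

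**Step 4. Compare like with like.** The 15% concerns in-person screening after consent. The q in step 3 covers everything up to randomisation, including exclusion at the baseline visit, a missed 21-day window and withdrawal. A bound on the first is not contradicted by a larger value of the second.

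**The case for a change.** The strongest case for acting is that the mismatch sits within one parenthesis of the current text, that the number was the very subject of the latest revision, and that the correction would take a sentence or two. The protocol nowhere calls 65 a maximum, gives a rate for later losses or states a margin, so the charitable readings are inferences. All of that stands as description: the basis for 65 is not written down, and the 15% alone does not supply it.

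What does not stand is the step from there to a faulty plan. The section never says that 65 was calculated from 15%. A consent number above the expected need is not an error in a single-site trial whose recruitment goal is stated separately as 44 randomised. The claim that the 15% understates the real loss needs observed screening results, and the documents contain none. The worry about the larger trial is also thin. Its planners will have the pilot's own count of children consented and randomised, which replaces any prior expectation. The feasibility definition under Aim 2 in section 14.0 uses tolerability, hypertension and tachycardia, not screening yield.

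**Conclusion.** No change to the plan follows. The stated rate gives an expected need of 52 consents against the 65 planned, a gap of 13, or of 8 to 9 against the 56 or 57 that a 90–95% margin would require. That gap is an unexplained allowance and not a contradiction. The three figures can all be true: 15% or fewer fail in-person screening, some further children are lost before randomisation, and 65 is set high enough that 44 are very likely to be reached.

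This rests on two assumptions. One is that recruitment is governed by the goal of 44 randomised, which the protocol repeats in sections 1.1, 4.1, 4.3 and 24.1. The other is that 65 is a limit or an allowance and not a number that must be filled. The binomial figures also treat children as independent with a common failure rate.

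If the 15% proves too low, the site's own enrolment records will show it, and those are the figures to carry into the larger trial. An added line on how 65 was reached would tidy section 9.1, but it would alter neither the number randomised nor any endpoint, estimate or conclusion.

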#### 10.0 Local Recruitment Methods

- 10.1 Recruitment Process: Recruitment will be achieved by a number of methods. These include mailing letters or sending electronic messages to potentially eligible participants within the MHealth Fairview Health System and our research partners, Children's Hospitals and Clinics of Minnesota and Health Partners/Park Nicollet health system. Direct recruitment of University of Minnesota Pediatric Weight Management clinic patients by Center for Pediatric Obesity Medicine CPOM clinician-scientists will also be conducted.
- 10.2 Identification of Potential Participants: Participants will be identified by using the University of Minnesota CTSI, Best Practices Integrated Informatics Core (BPIC) to identify patients in the MHealth Fairview health system based on age

PROTOCOL TITLE: Lisdexamfetamine for the Treatment of Severe Obesity in Children Aged 6 to 12 Years

VERSION DATE: 19Sep2025

and BMI. Both the recruitment mailing and the electronic messages will request that the interested parties contact the research staff for additional information. If the interested party and the research staff do not connect on the first try, the research staff will attempt to contact the interested parties with up to three follow-up phone calls and/or three emails.

- 10.3 Recruitment Materials: A recruitment letter and recruitment flyers will be created for this study and approved by the IRB before use.
- 10.4 Payment: Participation in this study is time intensive for the subject and their family members. Payment will be made by the Greenphire ClinCard to the parent on the following schedule:
  - Baseline visit: \$75 for the visit and \$25 when the accelerometer is returned
  - Week 4: \$75
  - Week 8: \$75
  - Week 12: \$75
  - Week 16: \$75
  - Week 20: \$75
  - Week 24 visit: \$100 for the visit and \$50 when the accelerometer is returned

Participants who complete all of the virtual lifestyle therapy visits will receive a \$100 bonus at the Week 24 visit. Therefore, participants will be eligible to receive a total reimbursement/compensation of \$725.

#### 11.0 Withdrawal of Participants

- 11.1 Withdrawal Circumstances: Participants will be allowed to withdraw from the study at any time. Participants will be asked to return for one final visit and to return any study medication. Participants may be withdrawn from the study at any time based upon investigator judgement.
- 11.2 Withdrawal Procedures: Any participant who is removed from the study by the principal investigator will be asked to return for one final visit to assess adverse events and to collect any unused study medication and do a final study medication compliance.
- 11.3 Termination Procedures: It will be noted in the subject enrollment log that the participant has been discontinued from the study and the date of the last study related visit. No additional data will be collected after that time. Data that has already been collected can be used in the study analysis.

PROTOCOL TITLE: Lisdexamfetamine for the Treatment of Severe Obesity in Children Aged

6 to 12 Years

VERSION DATE: 19Sep2025

11.4

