#### 14.0 Statistical Considerations

Data Analysis Plan: Descriptive analyses of baseline characteristics and outcomes will include means and standard deviations, median and range for continuous variables and frequencies with percentages for categorical variables. Safety analyses (including Barkley's Side Effect Rating Scale and incidence of hypertension and tachycardia) will be primarily descriptive reporting the number and percentage of adverse events during participation in the study. All safety outcomes will be evaluated and monitored throughout the study. Confidence intervals (Cis) and P-values for all analyses will be based on robust variance estimation. Statistical significance will be considered as p<0.05.

PROTOCOL TITLE: Lisdexamfetamine for the Treatment of Severe Obesity in Children Aged

6 to 12 Years

VERSION DATE: 19Sep2025

**Aim 1:** Estimate the treatment effect of LDX plus lifestyle therapy vs placebo plus lifestyle therapy on changes in BMI (%BMIp95 primary endpoint), body fat, cardiometabolic health and quality of life (QOL) from baseline to 24 weeks. **H1:** We hypothesize that LDX compared to placebo will result in a greater mean decrease in %BMIp95 and body fat, and improved cardiometabolic health and QOL at 24 weeks.

The primary outcome measurement will be absolute change in percent of the BMI 95th percentile abbreviated %BMIp95. Although we will report on other metrics of BMI change including absolute BMI change and percent BMI change, we chose %BMIp95 as the primary outcome measurement because of its clinical utility in measuring changes in BMI in young children who have severe obesity and a consensus in the research community that expressing BMI change relative to the 95th percentile is preferred over other metrics such as BMI standard deviation score a.k.a. z-score. The limitation of BMIz is explained by the flattening of BMIz curve at values significantly above the 95th percentile, despite the wide variance of BMIs in youth with severe obesity, which therefore leads to an underestimation of clinically significant improvement in weight status). The primary outcome will be the mean change in %BMIp95 from baseline to 24 weeks follow-up compared between treatment groups, while adjusting for baseline value for added precision. See Table 1 for examples of changes in BMI and corresponding changes in %BMIp95.

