14.1 Data Integrity: Impacting all aims, despite best efforts, it is possible that some data will be missing, which could limit the interpretation and generalizability of results. If the data are missing at random, conditioned on measured covariates, then supplementary analyses adjusting for these covariates will produce unbiased results. For potential missing data mechanisms beyond measured covariates, we will examine the extent to which results may be affected. Imputation techniques will be considered for missing data issues (e.g., multiple imputation). In particular, we will incorporate multivariate imputation by chained equations to handle missing data in follow-up visits. The imputation models will include baseline values and change from baseline. Additional variables for inclusion in the model include age, race, sex, Tanner stage, BMI, and LDX dose. We will also examine results without imputed values. If the analyses with and without multiple imputed values differ substantially, then exploratory analyses will be performed to evaluated factors that may have contributed to the differences.

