Adverse Event Reporting: The PI will be notified of all AEs within 7 days of identification; the PI will be notified of serious AEs (SAEs) within 24-hours of identification. A report of all SAEs will be sent to the FDA, the external medical monitor, DSMB,IRB, and NIH NIDDK program officer as soon as possible, but no later than five working days after the PI's initial receipt of the information. Reports of all adverse events, both serious and non-serious, will be provided to the external medical monitor and DSMB for review at their next regularly scheduled meetings.

Stopping Rules: In the event that a participant has an SAE that is deemed related to the study medication and/or procedures by the external medical monitor, DSMB, PI, and/or NIDDK, the participant will be required to immediately discontinue the study medication. However, the participant may be invited to stay in the study for lifestyle therapy if this seems beneficial to the participant and the SAE is not related to lifestyle therapy. Participants will be instructed that they may withdraw from the study at any time and for any reason. The overall study may be stopped at any time at the request of the external medical monitor, DSMB, PI, and/or NIDDK. Participants will be instructed that they may withdraw from the study at any time and for any reason.

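### Section 11.3 leaves no planned week-24 height and weight for a child whom the investigator removes from the study, although that family has refused nothing

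*Combined protocol and SAP*

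**What the plan says.** **Leaving the study.** Section 11.1 lets families withdraw whenever they wish and adds: "Participants may be withdrawn from the study at any time based upon investigator judgement". Withdrawing families are asked back once and asked to return drug. Under 11.2, a child removed by the principal investigator is "asked to return for one final visit to assess adverse events and to collect any unused study medication", with a last compliance check. Neither section lists height or weight at that visit. Section 11.3 then closes the record: "No additional data will be collected after that time". Data already collected may be used. The sentence has no exception by reason for leaving.

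**Related serious adverse event.** The Stopping Rules in 17.2 require study drug to stop, and then say that "the participant may be invited to stay in the study for lifestyle therapy if this seems beneficial to the participant", provided the event is not due to lifestyle therapy. They do not say whether a child who is not invited has left the study.

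**What continues.** Section 17.2 follows unresolved adverse events after the final visit, for 7 days if non-serious and 30 days if serious. Section 3.3 keeps in the trial a child who cannot tolerate even the smallest dose. Aim 2 in section 14.0 promises outcome capture whether or not the drug is tolerated.

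**Endpoint and missing data.** Aim 1 states: "The primary outcome will be the mean change in %BMIp95 from baseline to 24 weeks follow-up compared between treatment groups", with adjustment for baseline. Section 14.1 states: "we will incorporate multivariate imputation by chained equations to handle missing data in follow-up visits". It goes on: "Additional variables for inclusion in the model include age, race, sex, Tanner stage, BMI, and LDX dose". It also says: "We will also examine results without imputed values". For mechanisms beyond the measured covariates, it promises to examine how far results might change, but names no method.

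**The concern.** Stopping drug, leaving the visit schedule and refusing all further measurement are three different events. Section 11.3 treats every child discontinued from the study as if the third had happened. For a child removed on judgement it has not: the decision is the investigator's, and the family may be willing to attend for a height and a weight at week 24.

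The primary outcome is fixed at week 24. If the value is not sought, the child's result is either predicted by a model or left out. Both options lean on assumptions about why the child left. Removal on judgement may well depend on how the child was doing, and the variables that 14.1 names for imputation do not include the reason for leaving. The same week-24 height also feeds the height-velocity measure under Aim 2, so one short assessment would serve both aims.

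**Working it through.** **1. Ways of stopping, set side by side**

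| Situation | Governing text | Week-24 height and weight planned? |
|---|---|---|
| Smallest dose not tolerated | 3.3; Aim 2 | Yes, the child stays in the trial |
| Removed on investigator judgement | 11.1, 11.2, 11.3 | No; the exit visit lists neither measurement |
| Related serious adverse event, not invited to stay | 17.2 Stopping Rules; Aim 2 | Unclear; the text does not say whether this child has left the study |
| Family withdraws but would accept a measurement | 11.1, 11.3 | No; such families are not separated from those who refuse |
| Family refuses all further follow-up | 11.1, 11.3 | No, and rightly so |

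Only the second row is a clear loss of an obtainable value. The third and fourth are possible losses.

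**2. Inputs**

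- 44 children randomised 1:1 (section 1.1), so 44 / 2 = 22 per arm.
- Primary time point week 24 (Aim 1). Height and weight are already scheduled at that visit (section 7.3).
- Post-randomisation exit rate: not given. The 15% in section 9.1 is screening failure and is not used here.
- SD of the change in %BMIp95: not given. Section 14.0 states that the sample size does not come from a power calculation.

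No figure in the plan depends on this rule, so there is none to reproduce.

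**3. Weight of one child**

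1/22 = 0.0455, or 4.5% of an arm mean. If one child's imputed change misses the true change by e points, the arm mean moves by about e/22, which is 0.045 points for each point of error. Dropping the child gives the same formula, with e as the gap between that child and the rest of the arm.

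For scale only, assume e between 3 and 8.41 points. The upper value is borrowed from the 6-month mean change in the younger subgroup of the preliminary data (section 2.2).

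- 3/22 = 0.14 points per missing child
- 8.41/22 = 0.38 points per missing child

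**4. Precision without imputed values**

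With the same SD, losing k of 22 children multiplies that arm's standard error by sqrt(22/(22 − k)). The values of k are assumptions.

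- k = 1: sqrt(22/21) = 1.024, or +2.4%
- k = 2: sqrt(22/20) = 1.049, or +4.9%
- k = 3: sqrt(22/19) = 1.076, or +7.6%

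For the unadjusted difference between arms, one loss gives sqrt((1/22 + 1/21)/(2/22)) = 1.012, or +1.2%.

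**5. What cannot be computed**

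A total shift would need the number of such exits in each arm and the gap between leavers and stayers. The documents give neither. If both arms lose the same fraction with the same gap, the shifts cancel in the contrast.

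**The case against.** The case for leaving the text alone has five parts.

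- **The rule is softer than it sounds.** An exit visit is requested and unresolved adverse events are followed afterwards. This stands: a reader might infer that everything stops at once, and the documents do not support that. Neither provision yields a week-24 %BMIp95, however.
- **The adverse-event route is inferred.** A reader might take 17.2 to mean that every child with a related serious event who is not invited to stay drops out of the data. The text does not say so, and the Aim 2 promise could be read to cover that child. This stands; what the documents support is a need to reconcile the passages.
- **The family route is hypothetical.** Nothing shows how many withdrawing families would accept a measurement. The consent pages are not in the public version, so a choice offered there cannot be ruled out. Stopping when a family leaves a paediatric study is also a defensible default. This stands, and it is why the point rests on investigator removal.
- **Section 14.1 already deals with missing data.** A reader might infer that the plan ignores informative exit. It does not: it promises to examine mechanisms beyond measured covariates, and its list of imputation variables need not be closed. It also includes LDX dose, which may carry some information about intolerance. But no method is named, and no analysis stands in for an observed value that could have been had.
- **This is a pilot without a power target.** That lowers the stakes but does not remove them. Estimating the treatment effect is a stated purpose (section 1.1), and procedures here will inform the larger trial.

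A further tempting reading is that children who stop drug for intolerance are lost. Section 3.3 says the opposite.

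**Conclusion.** The point holds in a limited form. As written, section 11.3 gives up an obtainable week-24 primary endpoint for a child removed on investigator judgement, and it may do so on two other routes. Sections 3.3 and 14.0 (Aim 2) address tolerability and do not cure this.

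The size is unknown and may be small. Per missing child it is 4.5% of an arm mean and, without imputation, about 2.4% on that arm's standard error. These figures assume equal arms of 22 and an unchanged SD. A reader might infer that the treatment contrast is biased in a known direction. The documents give no exit rates, no SD and no evidence on how leavers differ, so no overall shift can be claimed.

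The change is worth making because it is cheap and lessens dependence on the missing-at-random assumption. It is not a fault that undermines the trial.

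**What to change.** 1. In 11.3, limit the sentence that ends data collection to cases where the family or the child refuses further follow-up.
2. Invite every other child who leaves the study to the height and weight assessment at the existing week-24 visit, and analyse the result in the randomised arm. Children who stop drug for intolerance need no new rule.
3. In 11.1 and 11.2, list height and weight at the exit visit. This reading supplements imputation and does not replace week 24.
4. Reconcile 11.3 with the Aim 2 promise of outcome capture, with the adverse-event follow-up in 17.2, and with the Stopping Rules, so that the study status of a child not invited to stay is clear.

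Nothing about when treatment stops should change.

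**Cost.** A protocol amendment is needed, probably with new consent wording and possibly re-consent of enrolled children. Section 10.4 pays $100 for the week-24 visit, so an assumed 1 to 8 children would cost 1 × $100 = $100 to 8 × $100 = $800. This lies within the 44 × $100 = $4,400 payable if everyone attended. Staff time and some family burden come on top. Intermediate readings after exit stay lost, and only children not yet past week 24 when the amendment takes effect can benefit.
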